8. PHARMACOKINETIC ANALYSIS

Pharmacokinetic (PK) assessments and analyses will be described in a separate [PK analysis plan](#).

9. PHARMACODYNAMIC ANALYSIS

The analysis of the bladder and bowel movement diary (BBMD) parameters will be based on the PD Analysis Set. All PD data will be captured on the BBMD. Subjects will enter BM-related information into a paper diary, the BBMD, on an event-driven basis (ie, following each BM) during the Screening Period (beginning at Day -8) and throughout the Clinic Period. The BM related information will include the day and time of BMs and a report of stool consistency for each BM using the BSFS (1=Separate hard lumps like nuts [difficult to pass], 2=sausage shaped but lumpy, 3=like a sausage but with cracks on surface, 4=like a sausage or snake, smooth and soft, 5=soft blobs with clear-cut edges (passed easily), 6=fluffy pieces with ragged edges, a mushy stool and 7=Watery, no solid pieces [entirely liquid]).

Subjects will complete the bladder portion of the BBMD in the morning of Dosing Day 1 (which represents the baseline responses) and in the morning of Discharge Day 2. The bladder diary will include the following questions:

In the past 24 hours...

- Did you have to urinate more frequently than normal? (yes/no)
- How many times did you urinate? (0 to 2; 3 to 6; 7 to 10; or more than 10)
- Did you feel the strong need to urinate with little or no warning? (yes/no)
- Did you have to get up to urinate during the night more frequently than usual? (yes/no)
- How many times did you have to get up at night to urinate? (0, 1, 2, 3+ times)
- Did you have pain or burning in your bladder or pelvic area? (yes/no)

9.1. Pharmacodynamic Analysis

Bowel movement data will be summarized by treatment for the baseline period and the 24-hour period after dosing using descriptive statistics. Change from baseline for the following BM parameters will be calculated:

- BM frequency
- Stool consistency (BSFS)

The baseline period for BM data is exactly 1 week and consists of the seven 24-hour periods that end at the time of first dose. Baseline values will be derived from the BBMD data collected during that period. The baseline BM daily frequency rate (BMs per day) will be calculated as the number of BMs the subject reports during this period divided by 7. Baseline stool consistency will be calculated as the average of the non-missing BSFS scores associated with the BMs reported by the subject during this period.

For BM data, the postdosing frequency and averages will be based on events and reports that occur during the 24-hour period that starts at the time of dosing and ends when subjects completes the BBMD 24 hours later on Day 2. Change from baseline will be defined as the postdosing values minus the baseline value. PD data will be provided in listings.

The PD data regarding bladder symptoms and urination is categorical. The baseline values are simply the responses to the 6 relevant questions asked, predose, in the morning of Dosing Day 1, and the postdosing values are the responses to the BBMD on Day 2.

For the bladder and urination data, shift tables by time point will be created for each of the 6 questions, showing the responses for the 24 hours before dosing (completed on the morning of dosing, Day 1) versus the responses for the 24 hours postdose (from Discharge, Day 2).

For the Day 1 BBMD diary, summary analyses will only include diaries that were completed before dosing. Any diaries that were completed after the first dose will not be used. Similarly, for the Day 2 BBMD diary, only diaries that were completed 20 hours or more after dosing will be used.

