4.1.1. Study Periods

4.1.1.1. Screening Period

The Screening Period will begin with the signature of the informed consent form (ICF) at the Screening Visit (which can occur from Day -28 to Day -8) and will last 7 to 27 days. At the Screening Visit, subjects will undergo preliminary screening procedures to ensure that they meet the inclusion and exclusion criteria for the study. Eligible healthy volunteers will receive the bladder and bowel movement diary (BBMD), a paper-based diary to complete on an event-driven basis (ie, for each BM) at home, and training on how to complete it to record their bladder and bowel habits. Subjects will complete the BBMD (BM portion only) daily only for the 7 days before Check-in on Day -1. The end of the Screening Period will coincide with the beginning of the Clinic Period at Check-in (Day -1).

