9.4.4. Exploratory Endpoints Analyses

PK analyses will be based on the PK Analysis Set.

Plasma concentrations of IW-3300 will be summarized by treatment (or cohort) at each assessment timepoint; additionally, a listing of plasma concentrations will be provided. PK parameters (as described in Section 8.5) will also be calculated for each subject and summarized by treatment, if systemic levels of IW-3300 are measurable/as data permit (≥ 1 plasma concentration above the lower limit of quantitation [LLOQ] is necessary for calculation of C_{max} and T_{max} ; ≥ 3 plasma concentrations above LLOQ are necessary for calculation of AUC_{0-t} , $AUC_{0-\infty}$, and $t_{1/2}$).

The total amount of IW-3300 in stool collected during the postdose collection period prior to Discharge will be summarized by treatment, including the concentration (ng/g; based on the wet weight of stool) and the percent recovery. Subjects who do not have a BM during the stool collection period will not be included in the analysis of IW-3300 in stool.

The analysis of the BBMD parameters will be based on the PD Analysis Set.

BBMD parameters (BM frequency, stool consistency, urinary frequency, urinary urgency, and nocturia) will be summarized by treatment (or cohort) for each study period (Screening Period and Clinic Period) using descriptive statistics and changes from baseline will be calculated whenever it is appropriate.

Baseline BM values will be derived from the BBMD data collected in the Screening Period, specifically, the period of time from 7 days prior to Check-in up to the time of randomization on Day 1. The baseline BM frequency rate (BMs per day) will be derived based on the number of BMs the subject reports during this period. The baseline stool consistency will be calculated as the average of the nonmissing BSFS scores associated with the BMs reported by the subject during this period.

The subjects reported assessments for urination category parameters (urinary frequency, urinary urgency, and nocturia) in the 24-hour period prior to drug administration on Day 1 will be used to establish the baseline for each urinary parameter. The subjects reported assessment of pain or

burning in the bladder or pelvic area in the 24-hour period prior to drug administration on Day 1 will be used to establish the baseline for this parameter.

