12.4. Bowel Movement Log

Study Visit: _____

Date: _____, _____, _____
 Month Day Year

Bowel Movements	
Did you have a Bowel Movement today?	 Yes  No
If yes, please complete the table below. Please complete one row below for each bowel movement (BM). If you have more than one BM in a day, please complete additional rows as needed. At the end of each day, please confirm that all BMs for that day have been entered and complete a row for each BM you may have forgotten to record.	
Time of Bowel Movement	Describe the bowel movement form (Please refer to the Bristol Stool Form Scale) Initials
_____ : _____	 AM  Type 1  Type 2  Type 3  Type 4  Type 5  Type 6  Type 7  PM
_____ : _____	 AM  Type 1  Type 2  Type 3  Type 4  Type 5  Type 6  Type 7  PM
_____ : _____	 AM  Type 1  Type 2  Type 3  Type 4  Type 5  Type 6  Type 7  PM
_____ : _____	 AM  Type 1  Type 2  Type 3  Type 4  Type 5  Type 6  Type 7  PM
_____ : _____	 AM  Type 1  Type 2  Type 3  Type 4  Type 5  Type 6  Type 7  PM
_____ : _____	 AM  Type 1  Type 2  Type 3  Type 4  Type 5  Type 6  Type 7  PM

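### SAP 9.1 divides baseline bowel movements by a fixed 7 with no rule for unfilled diary days, which can understate baseline and inflate within-group change; its baseline window also differs from the protocol's

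*SAP*

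**What the plan says.** SAP 9.1 fixes the BM baseline at one week, which "consists of the seven 24-hour periods that end at the time of first dose". The daily rate is "calculated as the number of BMs the subject reports during this period divided by 7". Postdose BMs are those "during the 24-hour period that starts at the time of dosing", and "Change from baseline will be defined as the postdosing values minus the baseline value".

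Protocol 9.4.4 uses another baseline window, "the period of time from 7 days prior to Check-in up to the time of randomization on Day 1". Its rate is "derived based on the number of BMs the subject reports during this period", with no divisor given.

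Before Check-in the data come from "a paper-based diary to complete on an event-driven basis" at home (protocol 4.1.1.1). The log in SAP 12.4 asks each day "Did you have a Bowel Movement today", with a Yes/No answer, before the rows for individual BMs.

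No minimum number of completed days appears anywhere. The Check-in review (schedule of activities, note h) tests only BM counts: three or more over Days -8 to -2, and no day above three. SAP 9.1 excludes Day 1 and Day 2 diaries by time of completion only. The conventions in SAP 12.1 cover repeated assessments, study day, partial dates and non-numeric laboratory results, but not diary days. The protocol's amendment history names the SAP as the place for incomplete-data rules.

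**The concern.** The numerator depends on what was written down; the divisor does not. If a subject had BMs on a home day but left the page blank, those BMs are lost while the day still counts among the seven. The day is scored as zero even though the Yes/No item could separate a true zero from a blank. Baseline stool consistency, by contrast, averages only the scores that are present, so among the BM measures only frequency treats a blank day this way.

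Under-recording is more likely before Check-in than after dosing. The first setting is a paper diary at home. In the second the subject is confined to the unit and all stool is collected. Because the endpoint is postdose minus baseline, BMs lost from baseline raise the reported change. BM frequency bears on diarrhea, the first risk listed in protocol 2.3.1, so an artificial rise would be read as a bowel effect.

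The two baseline windows are a separate matter. They give different baselines for the same diary, and the SAP does not flag the difference.

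**Working it through.** **1. The plan's own divisor.** 7 periods × 24 h = 168 h = 7.0 days. With every day recorded, dividing by 7 is correct for the SAP window.

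**2. Effect of unfilled days.** Let r be the true rate (BM/day), unchanged after dosing, and m the number of the seven days on which BMs occurred but nothing was recorded. Assume those days have the same rate as the others and that postdose recording is complete.

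- SAP baseline = r(7 − m)/7
- Spurious change = r − r(7 − m)/7 = r × m/7
- With divisor (7 − m): baseline = r(7 − m)/(7 − m) = r, and change = 0

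The documents give neither r nor m. Eligibility caps BMs at three per day. Spurious change in BM/day:

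| r | m = 1 | m = 2 | m = 3 |
|---|---|---|---|
| 1 | +0.14 | +0.29 | +0.43 |
| 2 | +0.29 | +0.57 | +0.86 |
| 3 | +0.43 | +0.86 | +1.29 |

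**3. Does the Check-in review stop this?** Take r = 1 with four unfilled days among Days -7 to -2. The diary shows 7 − 4 = 3 BMs, enough to pass the count. The SAP baseline is 3/7 = 0.43 and the spurious change 4/7 = +0.57. In a dose group of six, this one subject moves the mean by 0.57/6 ≈ +0.10.

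**4. Average effect under assumed blank rates.** With a morning dose the SAP window contains six home days (Days -7 to -2). If each is unfilled with probability q, the mean spurious change is r × 6q/7. At r = 1 this is +0.04, +0.09 and +0.17 for q = 5%, 10% and 20%.

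**5. Between arms.** The home days precede randomization, so the expected bias is the same in each arm. At r = 1, the chance imbalance between six active subjects and n pooled placebo subjects (8 from four cohorts, 10 from five) has SD = √[6q(1 − q)/49 × (1/6 + 1/n)]:

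- q = 10%: √(0.0110 × 0.292) = 0.06 for n = 8; √(0.0110 × 0.267) = 0.05 for n = 10
- q = 20%: √(0.0196 × 0.292) = 0.08 for n = 8; √(0.0196 × 0.267) = 0.07 for n = 10

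**6. The two windows.** The protocol window lasts 7 + (24 − c + z)/24 days, where c is the Check-in hour on Day -1 and z the randomization hour on Day 1. The clock times are assumptions. c = 18, z = 7 gives 7 + 13/24 = 7.5 days; c = 8, z = 11 gives 7 + 27/24 = 8.1 days. Counting from the start of Day -8 to 08:00 on Day 1 gives 8 + 8/24 = 8.3 days. With a morning dose the SAP window opens on the morning of Day -7 (there is no Day 0), so it drops Day -8 and takes in Day -1. Protocol 4.1.1.1 limits the home diary to the seven days before Check-in. It is therefore unclear whether BMs on Day -1 before arrival are recorded, although they fall inside the SAP window.

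**The case against.** Several points on the other side are sound.

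- The divisor matches the SAP window, and complete diaries give the right rate.
- A reader might infer that a blank day must lower the baseline and raise the change. The documents do not support that. BM entries are made per event, and eligibility allows as few as three BMs a week, so a blank may be a true no-BM day, for which zero is right. Postdose BMs are also self-recorded, and an omission there pushes the change down.
- Dividing by completed days can err the other way. A subject with three BMs on three days who leaves four true no-BM days blank has a correct SAP rate of 3/7 = 0.43. The completed-day rate is 3/3 = 1.0, which would hide a postdose rise.
- The Yes/No item refers to a calendar day, while the SAP periods run from dose time. A morning dose makes the window touch eight diary dates (Days -7 to -1 and Day 1), so a mapping rule is needed.
- There are safeguards: diary training, a Day -9 reminder call with replacement pages for subjects screened earlier, an end-of-day prompt to add forgotten BMs, staff review at Check-in, and confinement from Check-in onward.

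These points limit how often and how far the rule goes wrong, and they shape the remedy. They do not remove the gap: none requires seven completed days, and no rule says what a blank day means.

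**Conclusion.** The point holds in a limited form. The fixed divisor scores an unfilled home day as zero, so it can understate baseline and inflate within-group change in BM frequency by r × m/7. The amount depends on unfilled days that the documents do not quantify. At 1 BM/day it is +0.14 per such day, and averages +0.04 to +0.17 if 5% to 20% of home days are unfilled. The larger entries in the table need rates near the eligibility ceiling together with several unfilled days. The undeclared window difference is real but does not itself produce the inflation.

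Three stronger inferences are not supported:

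- **A false drug effect.** The expected bias is equal in placebo and active groups; only chance imbalance, with SD about 0.05 to 0.08 BM/day under the assumptions above, separates them. However, the plan summarizes change by treatment and specifies no placebo contrast that would cancel the shared part.
- **A baseline about 19% too high.** That comes from 8.3/7 = 1.19, which pairs the protocol's window with the SAP's divisor. Neither document does so.
- **An effect on safety decisions.** The endpoint is exploratory, no hypothesis is tested, and the primary endpoints are adverse event incidences. Protocol 7.1.1 bases suspension on related serious and graded adverse events, and protocol 2.3.1 has bowel habits monitored in real time. Nothing ties these to the derived SAP rate.

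It is still worth correcting, because a stated rule gives a wrong value in a foreseeable case and the data to avoid it are already collected.

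**What to change.** 1. Use one baseline window in both documents, or state in SAP 9.1 that its window is a change from protocol 9.4.4. Say whether BMs on Day -1 before Check-in are to be recorded.
2. Define the rate as BMs reported divided by the evaluable diary days in the window. A day is evaluable if the Yes/No item is answered or at least one BM is entered. State how calendar-day entries map to the dose-anchored periods, and count BMs over the same days as the divisor.
3. Have the existing Check-in diary review resolve each blank day as no BM or not recorded, so that true no-BM days stay in the divisor.
4. Set baseline to missing below a stated minimum number of evaluable days, and list evaluable days per subject.
5. Show the fixed-7 result as a sensitivity summary.

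Cost: a short paragraph in SAP 9.1, the mapping rule, modest programming and a small addition to the diary review. No new data item is needed. Some baselines will rest on fewer than seven days, and the rate will be overstated wherever true no-BM days stay blank. Items 3 and 5 are there to limit and expose that.

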2.3.1. Risk Assessment

Potential Risk of Clinical Significance	Summary of Data/Rationale for Risk	Mitigation Strategy
Study Intervention: IW-3300		
Potential for diarrhea and secondary dehydration	These are class effects of GC-C agonism or effects observed in nonclinical safety pharmacology and toxicology studies of IW-3300.	Intrarectal administration will likely decrease the risk of diarrhea and subsequent dehydration. The study design includes dose escalation to closely monitor subject safety and tolerability at each dose level before dosing with a higher dose; a Dose Escalation Committee will conduct blinded reviews of all the safety parameters of the dosing cohort through Discharge (Day 2) in order to make decisions regarding escalation to the next dose. Orthostatic vital sign measurements will be taken to evaluate the potential for volume depletion. The daily BM frequency and stool consistency will be monitored in real time to evaluate changes in bowel habits and the potential risk of diarrhea. Stopping rules will also be in place to evaluate continued dosing (Section 7.1.1); dosing within a cohort may be temporarily suspended in the event of a diarrhea or dehydration serious adverse event (SAE); ≥ 1 subject with Grade 3 diarrhea (increase from baseline of >7 stools per day and/or watery stools [BSFS score of 7] resulting in a limiting of self-care activities) or dehydration (hospitalization indicated); or ≥ 2 subjects with Grade 2 diarrhea (increase from baseline of 4 to 6 stools per day and/or watery stools [BSFS score of 7] resulting in a limiting of instrumental activities) or dehydration (intravenous fluids indicated).

Potential Risk of Clinical Significance	Summary of Data/Rationale for Risk	Mitigation Strategy

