5.1.2. Type of Subject and Disease Characteristics

2. Subject is medically healthy with no clinically significant findings during medical evaluation including physical examination, 12-lead ECG, and clinical laboratory tests (serum chemistry, hematology, urinalysis, and urine drug and alcohol screen). (NOTE: In making this determination, the investigator or designee will consider whether any finding could prevent the subject from performing any of the protocol-specified assessments, could represent a condition that would exclude the subject from the study, could represent a safety concern if the subject participates in the study, or could confound the study-specified assessments).
3. Subject has normal formed bowel movements (≥ 3 per week and ≤ 3 per day; average BSFS score of >2 and <6 , as reported in the BBMD during the 7 days before Check-in [Day -1]).
4. Subject agrees to refrain from making any new or major lifestyle changes (eg, new diet or exercise regimen) from the Screening Visit until after the Follow-up Phone Call on Day 14.
5. If subject is ≥ 45 years of age, subject is compliant with colorectal cancer screening guidelines according to the ACG Clinical Guidelines: Colorectal Cancer Screening 2021. (9)

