The Clinic Period values will be derived from the BBMD data collected after randomization in the Clinic Period, specifically, the period of time from Day 1 (postrandomization) through Day 2 (Discharge). The Clinic Period BM frequency rate will be derived based on the number of BMs the subject reports during this period. The Clinic Period stool consistency score is the mean of the nonmissing BSFS scores associated with the BMs reported by the subject during this period.

The subjects reported assessments for urination category parameters (urinary frequency, urinary urgency, and nocturia) in the 24-hour period after dosing on Day 1 will be used to establish the postbaseline assessments for each parameter. Subjects reported assessment of pain or burning in the bladder or pelvic area in the 24-hour period after dosing on Day 1 will be used to establish the postbaseline assessments for this parameter.

For the continuous variables, change from baseline will be defined as the Clinic Period value minus the baseline value. For the categorical variables, category shift from baseline to the Clinic Period will be assessed.

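### Stool consistency is tabulated only as each subject's average BSFS, so a diary-recorded watery stool (score 7) passed with firmer stools appears in no planned table unless it is reported as an AE

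*SAP*

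**What the plan says.** **Summary of stool form.** For the baseline week, SAP 9.1 states: "Baseline stool consistency will be calculated as the average of the non-missing BSFS scores". For the period after dosing it states: "For BM data, the postdosing frequency and averages will be based on events and reports that occur during the 24-hour period" starting at the dose. Protocol 9.4.4 defines the postdose value in the same way: "The Clinic Period stool consistency score is the mean of the nonmissing BSFS scores". Change from baseline is postdose minus baseline. SAP 12.1.1 summarizes continuous variables by n, mean, median, SD, minimum and maximum.

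**What is not planned.** Neither document plans a worst score per subject, a count of subjects with any score of 7, or a shift table for BSFS. Shift tables are planned only for the six bladder questions.

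**Use of score 7 elsewhere.** Protocol 2.3.1 puts it in the grading of diarrhea for the suspension rules. Grade 2 reads "increase from baseline of 4 to 6 stools per day and/or watery stools [BSFS score of 7] resulting in a limiting of instrumental activities". Grade 3 has a higher stool-count increase and/or "watery stools [BSFS score of 7] resulting in a limiting of self-care activities". The protocol's summary of changes says that FDA asked for a stool-consistency criterion.

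**Other routes for diarrhea.** SAP 7.1 tabulates TEAEs by preferred term, by CTCAE grade and by relationship. SAP 9.1 analyses BM frequency separately and lists the PD data. Protocol 2.3.1 provides for stools to be monitored in real time.

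**The concern.** BSFS is an ordered seven-category scale, and the category of most interest for this drug class is the top one. With 6 subjects per dose, the useful question is how many of them passed a watery stool. A mean of means does not answer it. The planned minimum and maximum do not recover the information either, because they are taken over subject averages rather than over stools.

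The SAP handles comparable data differently. Laboratory values, vital signs and ECGs (SAP 7.2 to 7.4) each get descriptive statistics plus the number and percentage of subjects crossing a threshold. Stool form gets only the first part.

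What is at stake is the bowel table of a first-in-human study. It could show a small shift in average form in a dose group where a third of subjects recorded a watery stool. If those stools were not reported as AEs, a reader would have to find them in the listings, with no tabulated comparison with placebo.

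**Working it through.** The plan gives no figure to reproduce: no sample size was calculated and no hypothesis is tested. The check is arithmetic on the planned summary.

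**Inputs**
- 6 active subjects per cohort (SAP 4.1.1).
- One watery stool (score 7) among *n* postdose BMs. The other stools and the baseline average are at score *b*. Both *n* and *b* are assumptions, varied below.

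**Formulas**
- Subject mean = (7 + b(n − 1)) / n
- Subject change = (7 − b) / n
- Group mean change with *k* of 6 affected and the rest unchanged = k(7 − b) / (6n)

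**Results for b = 4**

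| Postdose BMs (n) | Subject mean | Subject change | Group change, 1 of 6 | Group change, 2 of 6 |
|---|---|---|---|---|
| 1 | 7.0 | 3.0 | 0.50 | 1.00 |
| 2 | 5.5 | 1.5 | 0.25 | 0.50 |
| 3 | 5.0 | 1.0 | 0.17 | 0.33 |
| 4 | 4.75 | 0.75 | 0.13 | 0.25 |

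**Other values of b.** With b = 3 the subject mean is 5.0 (n = 2) or 4.33 (n = 3). With b = 5 it is 6.0 (n = 2) or 5.67 (n = 3). With 2 of 6 affected and n = 3, the group change is 0.44 for b = 3 and 0.22 for b = 5.

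**What the planned table would show.** Take two subjects with 7, 4, 4 and four unchanged at 4.
- The six changes are 0, 0, 0, 0, 1, 1.
- Mean change = 2 × 1.0 / 6 = +0.33. Median change = 0. Maximum change = +1.0.
- The largest subject value is 5.0. A subject with 5, 5, 5 also averages 5.0, so the table cannot separate a watery stool from uniformly softer formed stools.

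**What BM frequency adds.** If the two affected subjects have a baseline of 1 BM per day (assumed), three postdose BMs are +2 each, and the group change is 2 × 2 / 6 = +0.67. If a watery stool replaces a formed one, the change in frequency is 0.

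**What a count would show.** One affected subject appears as 1/6 = 16.7% (exact 95% CI 0.4% to 64.1%), and two as 2/6 = 33.3% (4.3% to 77.7%). If the true rate of any watery stool were 10%, 20% or 30% (assumed), the chance of at least one in six, 1 − (1 − p)^6, is 0.47, 0.74 or 0.88.

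**Subjects without a BM.** Entry allows as few as 3 BMs per week, or 3/7 = 0.43 per day, so some subjects may have none in 24 hours. They have no postdose average, but a yes/no item for any score of 7 is still defined for them.

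**Stool-count bands.** Protocol 2.3.1 gives increases of 4 to 6 for Grade 2 and above 7 for Grade 3. Baseline is a count divided by 7. A subject with 7 baseline BMs (1.00 per day) and 8 postdose has an increase of exactly 7. One with 10 baseline BMs (10/7 = 1.43 per day) and 8 postdose has 8 − 1.43 = 6.57. Neither increase falls in a band.

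**The case against.** A reader might infer from the averaging that the study could miss diarrhea, the main class effect. The documents do not support that. TEAE incidence is the primary endpoint, and diarrhea reported as an AE is tabulated by term, grade and relationship. Stools are monitored in real time, BM frequency is a separate parameter, and SAP 7.3 tabulates orthostatic indicators. With at most 40 subjects, the listings can be read subject by subject.

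A reader might also infer that score 7 by itself defines diarrhea. It does not. The grading text in protocol 2.3.1 ties watery stools to limitation of activities and/or a stool-count increase, and suspension under protocol 7.1.1 rests on related AEs and SAEs, not on the PD average.

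The examples also have limits:
- Subjects are encouraged to empty their bowels before dosing. A watery stool may then be the only postdose BM, giving a subject mean of 7.0 that shows as the maximum.
- In the 7, 4, 4 example the table would still show a maximum change of +1.0.
- Most of the diluted averages fall inside the entry criterion, "average BSFS score of >2 and <6", but that is a seven-day eligibility rule. No document uses it to judge postdose results.

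All of this stands, and it narrows the point. It does not close it. No rule in the documents turns a diary score of 7 into an AE. AEs are sought preferably by open-ended questions (protocol 8.3.2), and no AEs of special interest are defined (protocol 8.3.8). A watery stool that is recorded but not reported as an AE reaches the listings and no table of its own.

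**Conclusion.** The point holds in a limited form. The planned consistency summary is an average only, and it dilutes a score of 7 whenever the subject also passes firmer stools. What can go untabulated is diary-recorded watery stool that was not reported as an AE, and its comparison by dose with pooled placebo. In the worked case, 2 of 6 subjects (33.3%) with a watery stool appear as a mean change of +0.33 and a median change of 0.

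The size depends on the assumed score of the other stools and the number of postdose BMs. Across other-stool scores of 3 to 5 and three BMs, the group change with 2 of 6 affected runs from 0.44 down to 0.22. With a single BM there is no dilution.

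The weight is minor to moderate. The endpoint is exploratory and descriptive, and the SAP follows the protocol's own definition, so this is a cheap improvement rather than the correction of an error.

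**What to change.** Keep the mean and add to SAP 9.1, by dose and pooled placebo, for the 24 hours after dosing:
- n (%) of subjects with any BSFS 7;
- n (%) of subjects with any BSFS 6 or 7;
- the worst postdose BSFS per subject, with subjects who had no BM shown separately.

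For the two counts, use as denominator all PD Analysis Set subjects with a usable BM diary, and count those with no BM as no.

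Summarize the increase in BMs over the baseline daily rate numerically. Do not tabulate it in the bands of protocol 2.3.1, which leave increases above 6 up to and including 7 unassigned. Those bands must be reconciled before any use.

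The cost is SAP wording and one table from diary data already collected. Sample size and conduct do not change. One drawback is that expelled enema fluid may be scored as watery in either arm, and a yes/no count is more exposed to this than a mean. The counts must therefore be read against pooled placebo (up to 5 × 2 = 10 subjects).
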